10.4. Appendix 4: Study Phases, Study Periods, and Treatment Emergent Adverse Events

10.4.1. Study Phases and Study Periods

All assessments and events (including those collected as planned, early withdrawal and unscheduled visits) will be classified in study phases and study periods according to [Table 4](#) and [Table 5](#), respectively.

Assessments/events are assigned to study phases, and study periods sequentially, starting from the top of each table.

Table 4 Assignment of Study Phases

Study Phase	Definition
Screen	Assessments/Events assigned to Period=Screen in Table 5
OLI	Assessments/Events assigned to Period=OLI in Table 5
Injection	Assessments/Events assigned to Period=Injection 1 or Period=Injection 2 in Table 5
Follow-up	Assessments/Events assigned to Period=Follow-up in Table 5

Table 5 Assignment of Study Periods

For Adverse Events	
Study Period	Date range
Screen	If actual “Time of Day” for the assessment/event is collected:
	AE Start Date and Time < OLI Treatment Start Date & Time
	If actual “Time of Day” for the assessment/event is not collected:
	AE Start Date < OLI Treatment Start Date
OLI	If actual “Time of Day” for the assessment/event is collected:
	For participants continuing into Injection Phase: OLI Treatment Start Date & Time ≤ AE Start Date & Time < Date & Time of First CAB Injection
	For participants not continuing into Injection Phase: AE Start Date & Time ≥ OLI Treatment Start Date & Time
	If actual “Time of Day” for the assessment/event is not collected:
	For participants continuing into Injection Phase: OLI Treatment Start Date ≤ AE Start Date < Date of First CAB Injection
	For participants not continuing into Injection Phase: AE Start Date ≥ OLI Treatment Start Date
Injection 1	If actual “Time of Day” for the assessment/event is collected:
	For participants receiving second CAB injection: Date & Time of First CAB Injection ≤ AE Start Date & Time < Date & Time of Second CAB Injection
	For participants not receiving second CAB injection: Date & Time of First CAB Injection ≤ AE Start Date & Time and AE Start Date ≤ Date of Nominal Follow-up Week 4/Day 28 Visit [for Part 1 participants]/ Nominal Follow-up Week 12 Visit [for Part 2 participants]

	If actual “Time of Day” for the assessment/event is not collected: For participants receiving second CAB injection: Date of First CAB Injection ≤ AE Start Date < Date of Second CAB Injection For participants not receiving second CAB injection: Date of First CAB Injection ≤ AE Start Date ≤ Date of Nominal Follow-up Week 4/Day 28 Visit [for Part 1 participants]/ Nominal Follow-up Week 12 Visit [for Part 2 participants]
Injection 2	If actual “Time of Day” for the assessment/event is collected: Date & Time of Second CAB Injection ≤ AE Start Date & Time and AE Start Date ≤ Date of Nominal Follow-up Week 4/Day 28 Visit [for Part 1 participants]/ Nominal Follow-up Week 12 Visit [for Part 2 participants] If actual “Time of Day” for the assessment/event is not collected: Date of Second CAB Injection ≤ AE Start Date ≤ Date of Nominal Follow-up Week 4/Day 28 Visit [for Part 1 participants]/ Nominal Follow-up Week 12 Visit [for Part 2 participants]
Follow-up	AE Start Date > Date of Nominal Follow-up Week 4/Day 28 Visit [for Part 1 participants]/ Nominal Follow-up Week 12 Visit [for Part 2 participants]
For Injection Site Reaction Adverse Events (Where collected on the ISR form for study treatment associated reactions, including drug related and non-drug related)	
Injection 1	If actual “Time of Day” for the assessment/event is collected: For participants receiving second CAB injection: Date & Time of First CAB Injection ≤ AE Start Date & Time < Date & Time of Second CAB Injection For participants not receiving second CAB injection: Date & Time of First CAB Injection ≤ AE Start Date & Time If actual “Time of Day” for the assessment/event is not collected: For participants receiving second CAB injection: Date of First CAB Injection ≤ AE Start Date < Date of Second CAB Injection For participants not receiving second CAB injection: Date of First CAB Injection ≤ AE Start Date

Injection 2	If actual "Time of Day" for the assessment/event is collected:
	Date & Time of Second CAB Injection ≤ AE Start Date & Time and AE Start Date
	If actual "Time of Day" for the assessment/event is not collected:
	Date of Second CAB Injection ≤ AE Start Date
For PK Data	
Study Period	Data Range
OLI	Excluding Injection 1 Day 1 Pre-dose Samples: Start Date & Time < Date & Time of First CAB Injection
Injection 1	a) Injection 1 Day 1 Pre-dose Samples: Start Date & Time < Date & Time of First CAB Injection b) All Other Samples: For participants receiving second CAB injection: Date & Time of First CAB Injection ≤ Start Date & Time < Date & Time of Second CAB Injection For participants not receiving second CAB injection: Date & Time of First CAB Injection ≤ Date & Time and Start Date ≤ Date of Nominal Follow-up Week 4/Day 28 Visit [for Part 1 participants] / Nominal Follow-up Week 12 Visit [For Part 2 participants]
Injection 2	Date & Time of Second CAB Injection ≤ Date & Time and Start Date ≤ Date of Nominal Follow-up Week 4/Day 28 Visit [for Part 1 participants] / Nominal Follow-up Week 12 [for Part 2 Participants]
Follow-up	Start Date > Date of Nominal Follow-up Week 4/Day 28 Visit [for Part 1 participants] / Nominal Follow-up Week 12 Visit [for Part 2 participants]
Injection 2 Day 1 Pre-dose Samples: The original record will be assigned to Period = Injection 1 (as defined above). A duplicate record will be created and assigned to Period = Injection 2.	

Follow-up Week 4 [for Part 1 Participants], Follow-up Week 12 [for Part 2 Participants] Samples: If participant is not receiving second injection, the original record will be assigned to Period = Injection 1 (as defined above). A duplicate record will be created and assigned to Period = Follow-up. If participant has received second injection, the original record will be assigned to Period = Injection 2 (as defined above). A duplicate record will be created and assigned to Period = Follow-up.	
For Other Assessments (Excluding AEs and PK)	
Study Period	Date range
Screen	If actual "Time of Day" for the assessment/event is collected: Date & Time < OLI Treatment Start Date & Time If actual "Time of Day" for the assessment/event is not collected: Date < OLI Treatment Start Date
OLI	If actual "Time of Day" for the assessment/event is collected: For participants continuing into Injection Phase: OLI Treatment Start Date & Time ≤ Date & Time < Date & Time of First CAB Injection For participants not continuing into Injection Phase: Date & Time ≥ OLI Treatment Start Date & Time If actual "Time of Day" for the assessment/event is not collected: For participants continuing into Injection Phase: OLI Treatment Start Date ≤ Date < Date of First CAB Injection For participants not continuing into Injection Phase: Date ≥ OLI Treatment Start Date
Injection 1	If actual "Time of Day" for the assessment/event is collected: For participants receiving second CAB injection: Date & Time of First CAB Injection ≤ Date & Time < Date & Time of Second CAB Injection For participants not receiving second CAB injection: Date & Time of First CAB Injection ≤ Date & Time and Date ≤ Date of Nominal Follow-up Week 4/Day 28 Visit [for Part 1 participants]/ Nominal Follow-up Week 12 Visit [for Part 2 participants] If actual "Time of Day" for the assessment/event is not collected:

	
For ECG (inj 2 Day 1 pre-dose), Vital Signs (inj 2 Day 1 pre-dose), PK (inj 2 Day 1 pre-dose), Labs (inj 2 Day 1) Assessments: ^a
 
Date of First CAB Injection ≤ Date ≤ minimum of (Date of Second CAB Injection, Date of Nominal Follow-up Week 4/Day 28 Visit [for Part 1 participants]/ Nominal Follow-up Week 12 Visit [for Part 2 participants])
 
For Other Assessments/Events:
 
For participants receiving second CAB injection: Date of First CAB Injection ≤ Date < Date of Second CAB Injection
 
For participants not receiving second CAB injection: Date of First CAB Injection ≤ Date ≤ Date of Nominal Follow-up Week 4/Day 28 Visit [for Part 1 participants]/ Nominal Follow-up Week 12 Visit [for Part 2 participants]

Injection 2	Date of Second CAB Injection ≤ Date ≤ Date of Nominal Follow-up Week 4 Visit [for Part 1 participants]/ Nominal Follow-up Week 12 Visit [for Part 2 participants]
Follow-up	Date > Date of Nominal Follow-up Week 4 Visit [for Part 1 participants]/ Nominal Follow-up Week 12 Visit [for Part 2 participants]
For Preference Questionnaire (Cohort 4b)	
Study Period	Date range
Injection 2	Date ≥ Date of Nominal Follow-up Week 4 Visit

NOTES:

- Date = Date of assessment
- a. Pre-dose based on nominal planned timepoint variable (PTM)

Table 6 Study Phases for Concomitant Medication

Concomitant during:	Date range
Prior	Medication Taken < OLI Treatment Start Date
OLI	
For participants continuing into Injection Phase: OLI Treatment Start Date & Time ≤ Medication Taken < Injection Phase Treatment Start Date & Time
 
For participants not continuing into Injection Phase: Medication Taken ≥ OLI Treatment Start Date & Time

Injection 1	
For participants receiving second CAB injection: Date & Time of First CAB Injection ≤ Medication Taken < Date & Time of Second CAB Injection
 
For participants not receiving second CAB injection: Date & Time of First CAB Injection ≤ Medication Taken and Medication Start Date ≤ Date of Nominal Follow-up Week 4/Day 28 Visit [for Part 1 participants]/ Nominal Follow-up Week 12 Visit [for Part 2 participants]

Injection 2	Date & Time of Second CAB Injection ≤ Medication Taken and Medication Start Date ≤ Date of Nominal Follow-up Week 4/Day 28 Visit [for Part 1 participants]/ Nominal Follow-up Week 12 Visit [for Part 2 participants]
Follow-Up	Medication Taken ≥ Date of Nominal Follow-up Week 4 Visit [for Part 1 participants]/ Nominal Follow-up Week 12 Visit [for Part 2 participants]

NOTES:

- Please refer to [Appendix 7: Reporting Standards for Missing Data](#) for handling of missing and partial dates for concomitant medication. Use the rules in this table if concomitant medication date is completely missing.

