8. STUDY ASSESSMENTS AND PROCEDURES

- Study procedures and their timing are summarized in the SoA.

If these assessments are scheduled for the same nominal time, THEN the assessments should occur in the following order:

- 12-lead ECG
- vital signs
- blood draws.
- Protocol waivers or exemptions are not allowed
- Immediate safety concerns should be discussed with the sponsor immediately upon occurrence or awareness to determine if the participant should continue or discontinue study intervention.
- Adherence to the study design requirements, including those specified in the SoA, is essential and required for study conduct.
- All screening evaluations must be completed and reviewed to confirm that potential participants meet all eligibility criteria. The investigator will maintain a screening log to record details of all participants screened and to confirm eligibility or record reasons for screening failure, as applicable.
- Procedures conducted as part of the participant's routine clinical management (e.g., blood count) and obtained before signing of ICF may be utilized for screening or baseline purposes provided the procedure met the protocol-specified criteria and was performed within the time frame defined in the SoA.
- The maximum amount of blood collected from each participant over the duration of the study, including any extra assessments that may be required, will not exceed 500 mL
- Repeat or unscheduled samples may be taken for safety reasons or for technical issues with the samples.
- In Cohort 4b, participants will receive a topical NSAID or a topical steroid (high potency) as per the randomization schedule. These will be applied on Day -1 through to Day 5 after each subcutaneous abdominal injection.

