2.3. Study Design

Overview of Study Design and Key Features

Figure 2-1 Study Design Schematic – Part 1 (Cohorts 1-4):

a: active = CAB 400 mg/mL formulation

b: AC = Active control CAB 200 mg/mL formulation

c: At the VSLC meeting on 13 November 2020, it was agreed to modify the conduct of Cohort 2 based upon interim data: participants will receive a second subcutaneous abdominal injection of CAB 200 mg given as 0.5 mL CAB 400 mg/mL formulation or 100 mg as 1 x 0.5 mL CAB 200 mg/mL.

[figure not shown]
d: At their meeting on 22 December 2020, the STR agreed to reduce the dose of the first IM lateral thigh injection for remaining Cohort 3 participants based on interim PK data from Cohorts 1 and 2, i.e. CAB 400 mg given as 1 x 1 mL of CAB 400 mg/mL formulation or 400 mg as 1 x 2 mL CAB 200 mg/mL.

e: At their meeting on 22 December 2020, the STR agreed to conduct optional Cohort 4.

At a 22 December 2020 STR meeting, it was agreed

- to conduct Cohort 4 evaluating two 4-weeks apart (Q4W) injections of CAB 400 mg/mL 4 weeks apart (n=18, first injection 400 mg IM *gluteus medius* and second injection 200 mg SC) or two Q4W injections of CAB 200 mg/mL 4 weeks apart as active controls (n=2, first injection 400 mg IM *gluteus medius* and second injection 100 mg SC), and
- to reduce the dose of the first injection for the remaining Cohort 3 participants based on interim PK data from Cohorts 1 and 2. Participants yet to receive Injection 1# in Cohort 3 will receive CAB 400 mg given as 1 x 1 mL of CAB 400 mg/mL formulation or 400 mg as 1 x 2 mL CAB 200 mg/mL IM lateral thigh injection

[figure not shown]
Figure 2-2 Study Design Schematic – Part 1 (Cohort 4b):

Part 1 (Cohort 4b):

[figure not shown]
Cohort 4b will assess the PK, safety and **CCI** among 24 participants. All participants will receive two injections of 300 mg of CAB 400 mg/mL 4 weeks apart. **CCI**

CCI Participants (n=24) will be randomized according to a pre-generated randomization schedule to one of two sequences (i.e. 12 per sequence) of two treatments to be administered along with injection 1 and injection 2, respectively: **CCI**

Figure 2-3 Study Design Schematic – Part 1 (Cohort 4h):

Part 1 (Cohort 4h):

Cohort 4h will assess the PK, safety and tolerability of long-acting CAB 400 mg/mL and CAB 200 mg/mL formulations administered subcutaneously (abdominal) following recombinant human hyaluronidase PH20 (rHuPH20) administration.

Figure 2-4 Study Design Schematic – Part 2

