- Participants may be admitted to the clinic before Injection 1 Day 1 and Injection 2 Day 1. Any new Phase I unit participating in this study will adhere to the following SARS-CoV-2 testing procedures. **Where SARS-CoV-2 is circulating in the community**, participants should have one SARS-CoV-2 test approximately 1 week prior to admission to the clinic. A second test would be done upon admission; prior to the test result being known, participants should follow strict infection control procedures (PPE/social distancing) and should be isolated within an area of the unit to avoid exposure to COVID-19 negative participants until the test result is known. Once the test result is a confirmed negative, they can be released into the unit and follow infection control practices as per unit guidance. Any new Phase I unit participating in this study will adhere to the following SARS-CoV-2 testing procedures. A further test will be done on Day 8 upon discharge from the clinic. **Where SARS-CoV-2 is NOT circulating in the community**, SARS-CoV-2 testing prior to dosing may be performed within 5 days of admission to the clinic, and if participants are not admitted, they will be advised to avoid exposure to COVID-19 and self-quarantine until entrance to the unit while awaiting final testing clearance. Sponsor approval is required for site(s) to adopt SARS-CoV-2 testing within 5 days of admission to the clinic if study participants do not remain and isolate within the unit until test results are known. A further test is NOT required on Day 8 upon discharge from the clinic. Participants may have some assessments, such as HIV test, drug/alcohol screen, pregnancy test, haematology/chemistry/urinalysis and coagulation tests, done on the day before Injection 1 Day 1 and Injection 2 Day 1.
- CAB 400 mg/mL - injection 1 loading dose of 300 mg and injection 2 300 mg Q4W SC.

- AE assessment will include a brief, symptom-directed physical exam as needed.
A total of 38 PK samples will be collected through the injection phase and Follow-up.
Urine or plasma pregnancy testing to be performed pre-injection where relevant
HIV antibody test (either a laboratory or point of care test).
See Protocol Section 8.2.6.
See Protocol Section 6.1.2. The topical steroid or placebo will be applied once daily (midday) and the topical NSAID or placebo twice daily (morning and evening) from Day -1 to Day 5 for Injections 1 and 2.

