
 Calculated as the number of days from First Dose Date of CAB for the respective period (based on study period classifications in Table 5): 
Screening and OLI periods:
 
 If Assessment Date < First Dose Date of Oral CAB then 
 Period Day = Assessment Date – First Dose Date of Oral CAB If Assessment Date ≥ First Dose Date of Oral CAB then 
 Period Day = Assessment Date – First Dose Date of Oral CAB +1 
Injection 1 period:
 
 If Assessment Date < First Dose Date of Injection CAB then 
 Period Day = Assessment Date – First Dose Date of Injection CAB If Assessment Date ≥ First Dose Date of Injection CAB then 
 Period Day = Assessment Date – First Dose Date of Injection CAB +1 
Injection 2 period:
 
 If Assessment Date < Second Dose Date of Injection CAB then 
 Period Day = Assessment Date – Second Dose Date of Injection CAB If Assessment Date ≥ Second Dose Date of Injection CAB then 
 Period Day = Assessment Date – Second Dose Date of Injection CAB +1 
Follow-up period:
 
 If Assessment Date < Final Dose Date of Injection CAB then 
 Period Day = Assessment Date – Final Dose Date of Injection CAB If Assessment Date ≥ Final Dose Date of Injection CAB then 
 Period Day = Assessment Date – Final Dose Date of Injection CAB +1 
Where “Final Dose Date of Injection CAB” is the date of first CAB injection for participants who discontinue prior to receiving the second injection; otherwise this will be the date of the second CAB injection, if available.

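### Cohort 4b: topical courses start on Day -1 but SAP Table 5 opens AE periods at the injection, so non-ISR events from the first topical day are shown under the preceding period

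*SAP*

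**What the plan says.** Protocol Section 8 gives the timing of the topical products in Cohort 4b: "These will be applied on Day -1 through to Day 5 after each subcutaneous abdominal injection". The Cohort 4b schedule in SAP 10.2.1 marks topical administration on Day -1, and its footnote repeats the span: "from Day -1 to Day 5 for Injections 1 and 2".

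SAP 2.3 sets out the crossover. Participants are randomized to "one of two sequences (i.e. 12 per sequence) of two treatments to be administered along with injection 1 and injection 2, respectively". Within a sequence, then, the injection period identifies the assigned topical.

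SAP Table 5 assigns AEs to periods by onset:
- oral lead-in (OLI): "OLI Treatment Start Date & Time ≤ AE Start Date & Time < Date & Time of First CAB Injection"
- Injection 1, with time of day: "Date & Time of First CAB Injection ≤ AE Start Date & Time < Date & Time of Second CAB Injection"
- Injection 1, date only: "Date of First CAB Injection ≤ AE Start Date < Date of Second CAB Injection"
- Injection 2 opens at: "Date & Time of Second CAB Injection ≤ AE Start Date & Time"

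These AE rows apply to all cohorts. The only visible row in Table 5 specific to Cohort 4b is for the preference questionnaire. SAP 10.4.2 takes the treatment-emergent classification from the same table.

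**The concern.** The crossover treatment in Cohort 4b is the topical product, and exposure to it begins about a day before the injection that opens the matching period. A reaction to a first application is a natural tolerability question for such a product. Under the visible rules, a non-ISR event of this kind in the second course appears under the period of the other topical. In the first course it appears under oral lead-in, although oral dosing ended at least a week earlier.

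Such events would be recorded: Protocol 8.3.1 collects AEs from the start of intervention. The difficulty is only where they are then displayed. SAP 5.1 lists the two Cohort 4b sequences as separate arms, each with its own rows between oral lead-in and follow-up, so a sequence-by-period display would carry the misplacement.

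**Working it through.** The plan states no figure to reproduce. The check applies its date rules to the topical schedule.

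**Inputs.** Course span: Day -1 to Day 5 (Protocol 8; SAP 10.2.1). Participants: 24, with 12 per sequence (SAP 2.3). Period rules: SAP Table 5. Day numbering: SAP 10.6.1, which for a date before the second injection sets "Period Day = Assessment Date – Second Dose Date of Injection CAB" and adds 1 only from the injection date onward. There is no Day 0, so Day -1 is the calendar day before the injection.

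**Step 1: apply the rules.** For illustration the injections are 28 days apart at 09:00.

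| AE onset | Timed rule | Date-only rule | Topical in use |
|---|---|---|---|
| Inj 1 Day -1, after application | OLI | OLI | first |
| Inj 1 Day 1, before injection | OLI | Injection 1 | first |
| Inj 1 Day 1 after injection, to Day 5 | Injection 1 | Injection 1 | first |
| Inj 2 Day -1, after application | Injection 1 | Injection 1 | second |
| Inj 2 Day 1, before injection | Injection 1 | Injection 2 | second |
| Inj 2 Day 1 after injection, to Day 5 | Injection 2 | Injection 2 | second |

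Both rules misplace the Day -1 rows relative to topical exposure. The rules disagree with each other for the hours before the injection on Day 1. From the injection onward, both match.

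**Step 2: size of the window.** The application days are -1, 1, 2, 3, 4 and 5, which makes 6. One of them precedes the injection: 1/6 = 17% of application days. There are 24 × 2 = 48 courses. As a share of a 28-day injection period, the window is about 1/28 = 3.6%.

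**Step 3: effect of one event.** This assumes that the participant has no other event counted in the cells concerned.
- Sequence-by-period display: one participant in 12 is 1/12 = 8.3 percentage points in a cell.
- By-topical display, with 24 participants per topical: an event moved from the second topical to the first changes both counts, so the difference shifts by 2/24 = 8.3 points. An event moved to OLI leaves the comparison and shifts the difference by 1/24 = 4.2 points.

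The number of such events cannot be derived from the documents. A range of 0 to 3 is assumed. The 17% is a share of application days and says nothing about the share of AEs.

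**The case against.** A reader might infer that the crossover comparison of the two topicals is biased. The documents do not support that. The visible crossover endpoints are ISRs (SAP Table 2.42), the questionnaire displays (the PIN, NRS and preference shells among SAP Tables 2.45 to 2.48) and the ordinal preference endpoint (SAP 7.5.3). An ISR to an injection cannot precede it, so the injection is the right anchor for the ISR block of Table 5. Preference is collected after the second injection. No visible crossover endpoint uses non-ISR AEs.

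A reader might also infer that Day -1 events are blamed on oral cabotegravir. The OLI period in Table 5 runs through the washout up to the first injection, so it is a label of time and makes no causal claim.

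Other limits also stand:
- SAP 7.1 summarizes Cohort 4b safety by period, pooled over the topicals. In that display no event is credited to either product. Whether non-ISR AEs are also shown by topical is redacted in SAP 5.1 and 7.1. SAP 3.2 withholds results by topical for the interim analysis, which suggests, but does not show, that later displays give them.
- The change log (SAP 1.1) records added period derivation details for Appendix 4 with their subject redacted, and SAP 10.6.3 is partly redacted. A separate rule cannot be excluded, although the visible AE rows of Table 5 contain no exception.
- Simply moving the periods back to Day -1 would put events from before an injection into cabotegravir injection columns, against the safety objective and out of line with the other cohorts.
- The SAP footnote mentions matching placebo topicals, so a Day -1 reaction need not come from the active product.
- A local reaction entered on the ISR form would follow the ISR block, and the fix below would not move it.
- Every AE also appears in the full listing (SAP Listing 17).

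These points narrow the consequence. They do not alter the result that the visible rule places a non-ISR event from the first topical day outside the period of that topical.

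**Conclusion.** The point holds as a minor attribution problem. For Cohort 4b, the AE rows of Table 5 put non-ISR events with onset after the first application on Injection 2 Day -1 under Injection 1, and those on Injection 1 Day -1 under OLI. It concerns one of six application days per course in up to 24 participants, probably a few events at most, and only descriptive non-ISR summaries shown by sequence and period or by topical. The treatment-emergent classification inherits the same assignment.

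The conclusion rests on two assumptions: that no redacted rule overrides Table 5 for these events, and that at least one such display will be produced. It does not extend to the crossover endpoints or to the PK and laboratory results.

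**What to change.** For Cohort 4b non-ISR AEs, in any display by sequence and period or by topical, attribute the event to a topical from the first application of that course. No visible text shows that topical application times are recorded; if they are not, use the calendar day before the injection. Flag events with onset before the injection so that they are not read as following that cabotegravir injection.

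Keep the ISR, PK, laboratory and cabotegravir injection periods anchored on the injection. Concomitant medication (SAP Table 6) needs no change.

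The cost is one extra derivation and a footnote. The downside is that the Cohort 4b AE rows would differ slightly in definition from those of the other cohorts. If a redacted rule already does this, a cross-reference from Table 5 is enough.
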